10.2.13. Allocation of Trial Medication

During the single-blind run-in period (Week -2 and Week -1, inclusive) all participants will be allocated placebo. During the double-blind period (Week 1 to Week 4, inclusive) all participants will be allocated GMRx2 dose version 1(Triple ¼), GMRx2 dose version 2 (Triple ½) or placebo. Neither the site staff nor the participants will have foreknowledge of the treatment allocation at randomization. After the completion of the double-blind treatment period at Week 4, participants not entering the Open Label Extension Period will be switched to non-trial medication as per local guidelines/practice.

10.2.14. Dispensation of Trial Medication

Starting at the screening visit (Week -2), participants will receive sufficient quantities of the trial medication until the next scheduled trial visit. In the case of dispensed treatment lost/damaged, participants will be asked to notify the site immediately and replacement treatment will be dispensed by the site. In circumstances where a participant is unable to return to the site to collect replacement trial medication between the two scheduled trial visits, trial medication delivery will be arranged to the participant's location. Delivery of trial medication to the participant's location may also occur in other circumstances and where feasible e.g. if blood test results are not available at the time of the randomization visit and/or dispensing is delayed or due to pandemic restrictions. Sites will maintain accurate and up to date records of all trial medication dispensation to participants. Such records must be available for inspection at all times.

10.2.15. Returning of Trial Medication

Trial participants will return all unused randomized trial medication to the sites at Week 4 (or prior in some circumstances – e.g. discontinuation of treatment) and at respective visits for the open label extension period. Sites will collect all the returned trial medication and keep an accurate record for inspection at all times.

10.2.16. Concomitant Treatments

Starting at the screening visit, during all scheduled and unscheduled visits until the end of participation, the investigator/site will review participant concomitant treatments and update the relevant section in source documents and electronic case report form (eCRF) keeping in view the trial allowed and prohibited concomitant treatments. Prescription of non-trial BP-lowering drugs will only be allowed as noted in Section 8.6, page 23. Treatment with other drugs that do not affect BP significantly will be unrestricted and will be at the discretion of the treating physician. For the prescription of concomitant treatments, contraindications and drug-drug interactions should be taken into consideration as per the regulatory-approved prescribing information of drug prescribed. All other medical care should be delivered according to local guidelines/standards by the treating physician.

10.3. Visit details

10.3.1. Pre-Screening Visit (as required)

- Can be conducted over the phone.
- Assess potential participant's interest for participation and eligibility for the trial.
- Discuss the trial with the potential participant, including using the PISCF, and obtain signed informed consent. Potential participants may be provided time to consider their participation, with a follow-up visit arranged as needed.
- Consider stopping current BP monotherapy to facilitate trial eligibility, if clinically appropriate and considered safe. Informed consent must be obtained before the modification of medication.
- If locally preferred and/or feasible, blood tests can be pre-arranged following informed consent.
- The pre-screening visit can be repeated up to 3 times, as needed

10.3.2. Screening Visit

- Assess the potential participant's interest and eligibility for the trial.
- Discuss the trial with the potential participant, including using the PISCF, and obtain signed informed consent. This can also be done before the screening visit. The potential participant can be given the opportunity to consider information and return within the time window for randomization.
- Collect demographic information.
- Collect information on medical history, perform a physical examination.
- Review all medication currently being taken.
- Measure height and weight.
- Measure BP and pulse.

- Perform 12-lead ECG.
- Collect blood and urine samples, including for pregnancy, (if applicable) or arrange for these tests to be completed during the run-in period. Results must be reviewed and eligibility confirmed prior to randomization, but are not required for review prior to the beginning of the placebo run-in.
- Collect sub-study blood and urine samples (if applicable) – these can also be collected during run-in or at the randomization visit if preferred.
- Assess eligibility as per the trial inclusion and exclusion criteria.
- Consider stopping current BP monotherapy to facilitate trial eligibility, if clinically appropriate and considered safe. Informed consent must be obtained before the modification of medication. If medication is altered, a period of at least 14 days is required between alteration of BP treatment and trial randomization (ie the minimum placebo run-in duration is 14 days). In situations in which it is not deemed clinically appropriate to stop BP monotherapy for the trial duration, such participants should be regarded as ineligible.
- Demonstrate home BP measurement and dispense home BP monitor (record serial number) to participant.
- Dispense run-in medication as soon as possible.

10.3.3. Re-Screening

Participants can be re-screened up to three times in total during the recruitment period. Participants not meeting the eligibility criteria at Pre-Screening or Screening Visit can be re-screened if the reason for non-eligibility was transient (e.g. a short-term illness, abnormal laboratory finding, etc.), or if eligibility is expected to change (e.g. due to an alteration in BP regimen), or a remediable non-medical issue prevented completion of run-in (eg. BP machine malfunction). However, participants cannot be re-screened if they were intolerant of the run-in medication, if they required add-on medication during run-in or if valid home BP measurements did not meet criteria for randomization. Before re-screening, a new consent must be signed if more than 2 months have elapsed since signing the consent the first time. All eligibility criteria must be re-assessed on re-screening. Trial-specific laboratory investigations results available from within 30 days of the date of re-screening may be used to assess eligibility for trial participation.

10.3.4. Extended Run-In

The run-in period can be extended by up to 1 week if needed for reasons such as technical issues with the BP machine or measurement protocol or administrative issues, such as a delay in receiving test results. However, the run-in period cannot be extended if the treatment was not tolerated or if valid home BP measurements did not meet criteria for randomization. If the run-in is extended, participants should measure home BP in the 4 days prior to the new Randomization Visit date.

10.3.5. Randomization Visit

- Measure BP and pulse.
- Record any AESIs/SAEs that have occurred since the screening visit.
- Collect unused run-in medication.
- Assess adherence to run-in medication.
- Assess adherence to home BP monitoring schedule.
- Record all medication currently being taken by the participant.
- Review laboratory results. If laboratory results are not available for review prior to or on the same day end of the randomization visit, randomization must be delayed until the results are available and eligibility has been confirmed. If eligible, the participant will either be required to return to the clinic for the collection of randomized treatment, or alternatively, if feasible according to local practice and if the participant consents, the randomized medication may be delivered by courier to the participant's home.

- Collect sub-study urine and blood for storage (if applicable and not collected during the run-in period).
- Review home BP measurement technique.
- Assess eligibility as per the trial inclusion and exclusion criteria.
- Confirm that participant is suitable to be randomized. If not, collect home BP monitor and thank for participation. If suitable, randomize participant.
- Dispense treatment according to the allocated kit number selected by IBM database (eCRF).
- Advise participant to visit the site 1 or 7 days before the Week 4 visit for the placement of the ABPM device, if participating in ABPM substudy.

10.3.6. ABPM Device Placement Prior to Week 4 Visit (if applicable)

- To be conducted 1-7 days prior to Week 4 Visit
- Initialize and program the ABPM device, place on the participant and provide instructions on use.
- Instruct the participant to return the device to the site after completing 24 hours of ABPM.

10.3.7. Week 4 Visit

All participants

- If applicable, collect the ABPM device, download the data, check if 24-hour ABPM was successful. If unsuccessful, repeat within 48 hours and delay the Week 4 visit.
- Measure BP and pulse.
- Record AESIs/SAEs since the previous visit.
- Collect fasting blood and urine samples.
- Collect sub-study urine and blood for storage (if applicable)
- Review all medications being taken by the participant and update concomitant medications.
- Collect unused trial medication and review medication adherence

If the site is participating in Open-Label extension, invite all participants still receiving trial medication to participate.

Participants continuing in the Open-Label Extension period – go to Section 10.3.9

Participants not continuing in the Open-Label Extension period:

- Collect home BP monitor.
- Ask participants to report any AEs during the next 4 weeks after the end of trial medication.
- Record AESIs/SAEs since the previous visit.
- Collect blood and urine sample
- Review all medications being taken by the participant and update concomitant medications.
- Stop trial medication and prescribe alternate BP-lowering treatment in line with local guidelines/practice.
- Explain that the trial follow-up is now completed and thank participant.

10.3.8. Week 8 visit (End of Trial Visit for participants not continuing in the Open-Label Extension Period)

- Contact participant by telephone.
- Record AESIs or SAEs since the previous visit.
- Review all medications being taken by the participant and update medications.
- Arrange blood and urine for participants who have had $\geq 30\%$ reduction in eGFR and/or $\geq 30\%$ increase in serum creatinine between baseline and week 4 visits
- Explain that the trial follow-up is now completed and thank participant.

10.3.9. Week 4 Commence Open-Label Extension Period (selected sites only)

- Obtain consent for Open-Label Extension Period
- Switch from randomized treatment to Open-Label GMRx2 Dose1, as outlined in 8.4.3, page 22.

- For a device will be collected and new BP monitor will be issued

10.3.10. Week 6, 8, 16, 28, 40 (for Open-Label Extension Period only)

- Measure clinic BP and pulse.
- Record AESIs/SAEs since the previous visit.
- Arrange blood and urine for participants who have had $\geq 30\%$ reduction in eGFR and/or $\geq 30\%$ increase in serum creatinine between baseline and week 4 visits (Week 8 only)
- Collect blood sample (Week 16, 28).
- Review all medications being taken by the participant.
- Collect unused study medication (if applicable).
- Continue medication as is or titrate according to GMRx2 treatment regimen
- Dispense study medication (if applicable).

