3. Pregnant or had a positive pregnancy test or unwilling to undertake a pregnancy test during the trial and up to 30 days after the discontinuation of the trial medication or breastfeeding or of childbearing age and not using an acceptable method of contraception (defined in the Manual of Procedures). Acceptable methods of birth control include hormonal prescription oral contraceptives, contraceptive injections, contraceptive patch, intrauterine device, double-barrier method (e.g. condoms, diaphragm, or cervical cap with spermicidal foam, cream, or gel), or male partner sterilization. Contraception should be used for at least 1 month before the Randomization visit and until the end of trial participation.
4. Current estimated glomerular filtration rate (eGFR) <60 ml/min/1.73m.²
5. Electrolyte levels that would be regarded as contraindications for any of the potential treatment arms e.g. serum sodium <132mmol/l or >148 mmol/l or serum potassium <3.1 mmol/l or >5.6mmol/l.
6. Current/history of aspartate aminotransferase (AST) or alanine aminotransferase (ALT) >3 times the upper limit of normal range within 6 months.
7. Any abnormal laboratory value which in the judgment of the investigator could interfere with the effective conduct of the trial or constitutes a significant risk to the participants' safety or well-being.
8. Fulfilling any of the exclusion criteria mentioned for the screening visit, when verified again at the randomization visit.

At week 4 (for optional Open-Label Extension Period)

1. Contraindication to open-label GMRx2-based BP-lowering treatment.

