8.4.3. Optional Open-Label Extension Period

In a subset of sites, participants who are still receiving study medication at Week 4 will be invited to continue on to an optional Open-Label Extension Period with the aim to assess effectiveness, safety and adherence over a 52-week period. Willing participants will enter the Open-Label Extension Period at the Week 4 visit, at which time they will be allocated open-label GMRx2-Dose version 1. Follow-up visits will be conducted at Week 6, 8, 16, 28, 40, and end of Open-Label Extension Period visit at week 52 (See Table 6). Participants will continue to monitor BP at home, once per week until the Week 8 visit, and thereafter on a set day every month (e.g. 1st day of the month) until the week 52 visit. Home BP measurements will be made using a validated, electronic, automatic, digital upper-arm cuff and recorded in a home BP diary, as specified in the Blood Pressure Monitoring Manual of Procedures. During follow-up visits, if home BP from the most recent measurement is above 130 mm Hg for SBP and/or above 80 mmHg for DBP, BP-lowering therapy will be up-titrated in the following order: GMRx2-Dose1 → GMRx2-Dose2 → GMRx2-Dose3 (telmisartan 40mg/amlodipine 5mg/indapamide 2.5mg) → GMRx2-Dose3 plus telmisartan 40 mg/amlodipine 5 mg → GMRx2-Dose3 plus telmisartan 40 mg/amlodipine 5 mg plus spironolactone 25 mg. The rationale for this regimen is based on the evidence indicating that:

- About 80% of the maximum BP-lowering effects of BP-lowering regimens are achieved by 2 weeks⁵⁰
- US hypertension guidelines recommend a home BP target of <130/80 mmHg²⁵
- Up-titration steps should provide clinically meaningful BP reductions – the BP reductions of only 2-3/1-2 mmHg achieved by increasing the dose of a single drug are likely to be only modestly effective and such steps can act as barriers to effectively achieving BP goals.⁵⁰ Doubling the dose of telmisartan 40 mg/amlodipine 5 mg achieves an additional 5/4 mmHg reduction,⁵¹ and the use of concomitant ARB therapy reduces the incidence of pedal oedema associated with higher dose amlodipine.^{59,61} The Pathway-2 trial demonstrated that a mineralocorticoid receptor antagonist is superior to a beta-blocker or an alpha-blocker in patients not controlled on maximal doses of three drugs.⁶²

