³ The following blood and urine tests should be taken at a time most suitable for the participant at Screening visit or during run-in so that results are available for review at the RAND visit, and during Week 4 (ie. at the week 4 final visit or in the preceding week):

- Fasting glucose
- Fasting lipid profile (total cholesterol, low-density lipoprotein cholesterol, high-density lipoprotein cholesterol)
- HbA1c - for participants with diabetes without a HbA1c in past 3 months; repeat measure not required at Week 4
- Complete blood count (red blood cell count, hemoglobin, hematocrit, mean corpuscular volume, reticulocyte count, white blood cell count, platelet count)
- Liver function (bilirubin, albumin, total protein, gamma-glutamyl transferase, alkaline phosphatase, aspartate transaminase and alanine transaminase)

- Sodium, potassium, chloride
- Calcium
- Creatinine with eGFR
- Uric acid
- Thyroid-stimulating hormone; repeat measure not required at Week 4
- Blood sample for storage for substudy (if participating)
- Urine albumin-creatinine ratio
- Urine sample for storage for substudy (if participating)

All laboratory investigations and ECG will be performed at the trial site or local laboratory. If blood test results are not available on the same day as the randomization visits, once eligibility has been confirmed, participants may need to return to the clinic to collect the trial medication and home BP monitor. Alternatively, where feasible and consent from the participant received, trial medication and home BP monitor may be couriered to the participant's home once eligibility is confirmed.

⁴At Week 8, only for participants who have had ≥30% reduction in eGFR and/or ≥30% increase in serum creatinine between RAND and Week 4 visits

⁵If participating in Open-Label extension phase, see Table 6 for additional assessments at Week 4 and thereafter

* If a screening visit is rescheduled, then the randomization date should be scheduled/rescheduled so that the length of the run-in period remains at least 12 days. Option to extend run-in by up to 1 week if there have been technical or administrative issues with BP machine use and or measurement protocol. Ideally there should not be a gap between the end of Run-in period and Randomization. Post-randomization visit dates should not be altered i.e. should remain at the scheduled time since randomization.

EOT=End of trial; FU=Follow up; PRESCREEN=Pre-screening; RAND=Randomization; SCREEN=Screening

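### Minor, extension only: Protocol 10.3.10 contradicts Table 6 on safety bloods at Weeks 8 and 28, so a site using 10.3.10 could titrate twice with no routine electrolytes between Week 4 and Week 16

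*Protocol*

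**What the plan says.** Participants who enter the extension do so at the Week 4 visit, "at which time they will be allocated open-label GMRx2-Dose version 1" (Protocol 8.4.3). At later visits the dose goes up "if home BP from the most recent measurement is above 130 mm Hg for SBP and/or above 80 mmHg for DBP". The sequence runs from Dose 1 to Dose 2 to Dose 3 and then to add-on drugs. Section 10.3.10 repeats the action for Weeks 6, 8, 16, 28 and 40: "Continue medication as is or titrate according to GMRx2 treatment regimen".

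Two places set the blood tests for these visits:

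- **Table 6.** Section 10.1 names it as the schedule from Week 4 for people in the extension. Its rows for sodium/potassium/chloride and for creatinine with eGFR are ticked at Weeks 8, 16 and 52, with no condition. Footnote 2, which restricts testing at Week 8 to participants with a change of at least 30% in eGFR or creatinine, is attached to the two urine rows only.
- **Section 10.3.10.** It arranges Week 8 blood and urine for participants with that 30% change between baseline and Week 4, and otherwise lists a blood sample at Weeks 16 and 28. The Week 52 sample is in 10.3.11.

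The Week 8 line in 10.3.10 is nearly identical to one in 10.3.8. That section covers the Week 8 telephone call to participants who left trial medication at Week 4.

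**The concern.** The 30% condition suits 10.3.8, where treatment has stopped and the only question is whether an abnormal kidney result has recovered. In 10.3.10 it applies to people who are taking a thiazide-like diuretic with an angiotensin receptor blocker, and whose dose may be rising. There it has two weaknesses. It does not look at sodium or potassium. It also compares two values taken before the extension began, which for a former placebo participant are both off-drug.

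A site that works from the visit instructions rather than the table could therefore omit Week 8 electrolytes in anyone with stable creatinine. Protocol 5.7 recognizes that diuretics can cause hypokalemia, while noting that telmisartan reduces it. There is also a small reporting cost. Section 9.3 promises descriptive safety outcomes for the extension cohort, and Week 8 laboratory data would be incomplete if sites followed different instructions.

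**Working it through.** **1. The two schedules side by side** (Table 6 ticks assigned by counting its seven visit columns)

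| Visit | Table 6: electrolytes, creatinine/eGFR | 10.3.10 (Week 52: 10.3.11) |
|---|---|---|
| Week 6 | none | none |
| Week 8 | all participants | only after a ≥30% eGFR or creatinine change |
| Week 16 | all participants | all participants |
| Week 28 | none | blood sample, tests not named |
| Week 40 | none | none |
| Week 52 | all participants | all participants |

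Of the five visits in 10.3.10, Weeks 8 and 28 differ: 2 of 5.

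**2. Is the column count safe?** The consent row falls at Week 4 only and the clinic BP row at Weeks 6 to 52, as expected. Moving the blood rows one column to the right, in order to match 10.3.10, would push the Week 52 tick off the table. The blood rows therefore read cleanly. The urine rows do not: their footnoted tick falls under Week 16 in the extracted text, although the footnote speaks of Week 8. That needs a look at the PDF.

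**3. Time without routine electrolytes.** The windows are ±7 days at Weeks 4 and 8, and ±14 days at Week 16. I assume that they run from randomization. The footnote to Table 5 says that visit dates "should remain at the scheduled time since randomization", and Table 6 is silent.

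- Week 4: day 28, range 21 to 35. Week 8: day 56, range 49 to 63. Week 16: day 112, range 98 to 126.
- Week 4 to Week 8 (Table 6): 56 − 28 = 28 days; range 49 − 35 = 14 to 63 − 21 = 42.
- Week 4 to Week 16 (10.3.10, no 30% change): 112 − 28 = 84 days; range 98 − 35 = 63 to 126 − 21 = 105.

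**4. Dose reached in that time.** Two steps are possible: Dose 1 to Dose 2 at Week 6, and Dose 2 to Dose 3 at Week 8. Indapamide would go from 0.625 to 1.25 to 2.5 mg, and 2.5 / 0.625 = 4 times the entry dose. Nominal time on Dose 3 before the Week 16 draw is 112 − 56 = 56 days.

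**5. Former placebo participants.** Placebo is 50 of the 250 planned, or 20%. Their baseline and Week 4 samples both precede any GMRx2, so the trigger carries no information on its effect. Their first routine electrolytes on GMRx2 come nominally 28 days after starting under Table 6, and 84 days after under 10.3.10.

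**The case against.** The best defence is that 10.3.10 does not restrict Week 8 blood in so many words. It says whom to arrange tests for, and it could be read as extra follow-up on top of Table 6, which 10.1 makes the extension schedule. That reading is possible, but 10.3.10 then still lists no routine Week 8 draw, although it does list routine draws at Weeks 16 and 28. Week 28 remains unmatched on any reading.

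A second defence is that a footnote mark may have been lost from the blood rows of Table 6, since the matching footnote in Table 5 does attach to follow-up creatinine. This is unproven, and the marks on the urine rows did survive. If it were so, the Week 8 contradiction would shrink, but the safety gap would then lie in both places.

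Several mitigating facts stand:

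- Everyone enters at the lowest dose, so participants from the Dose 2 arm step down at Week 4, and a Week 6 increase returns them to a dose already taken.
- Participants were screened on eGFR and electrolytes before randomization.
- The dose can be stepped down or stopped.
- Table 6 leaves the timing of draws to local practice and any other tests to the investigator.

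A reader might go further and infer that the dose can be raised at Week 6 with the Week 4 results unread, because those bloods may be drawn "at the week 4 final visit or in the preceding week", the switch to Dose 1 happens at the same visit, and titration depends on home BP. The documents do not support that. Abnormal sodium, potassium, creatinine or eGFR is an adverse event of special interest (17.1.2). Such events are asked about at every visit and the action taken on medication is recorded (17.2.3). In 10.3.10 that recording comes before titration, and the 30% rule itself presupposes that the Week 4 creatinine has been read. An explicit sentence would be an optional clarification, not the repair of a defect. This safeguard does not answer the Week 8 point, because an abnormality cannot be recorded from a sample that was not taken.

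**Conclusion.** The contradiction is real, and it is minor. Section 10.3.10 and Table 6 give different blood-test instructions at Weeks 8 and 28. At Week 8 the version in 10.3.10 is the less safe one: a site following it could titrate at Weeks 6 and 8 with no routine electrolytes between Week 4 and Week 16, nominally 84 days. The documents do not show that any site did so, and sites may in practice follow Table 6. The number affected cannot be estimated, because extension entry and the instruction that sites used are not given.

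The conclusion rests on the extracted column positions of the blood rows in Table 6, which hold up on checking, and on visit windows that run from randomization. The extension is optional, runs at a subset of sites, and is analyzed under a separate plan (SAP 3.5.3), so the Week 4 efficacy and safety comparisons are unaffected.

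**What to change.** Amend 10.3.10 so that sodium, potassium and creatinine/eGFR are collected at Week 8 from all extension participants, as Table 6 already schedules. Keep the 30% condition for the Week 8 urine tests only. Decide whether a Week 28 blood sample is wanted, and make 10.3.10 and Table 6 agree. Before editing, check in the PDF where the footnoted urine ticks sit and that the blood rows carry no footnote.

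The cost is a wording change. Week 8 needs no test beyond Table 6, and treatment is not interrupted. If Week 28 is kept, it becomes an addition to Table 6; if it is removed, nothing that Table 6 schedules is lost.
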